8.1.2 Initial Visit Day: Screening/Enrollment

The subject will have the option to discuss with the study coordinator over the phone or by a Zoom teleconference from the subject's personal device. If Zoom communication is selected a unique meeting number and password known only to the subject will be provided. The study coordinator will monitor the number of attendees in the meeting and restrict meetings to IRB approved researchers on this study, the study subject, and additional people at the subject's discretion. Researchers will host the Zoom sessions and will utilize the waiting room feature to ensure that only the appropriate participants are included on the call.

The study coordinator will cover following topics associated with the study during the Screening/Enrollment visit:

STU#: STU00214445

- (1) Informed Consent will be reviewed and signed electronically using REDCap.
- (2) The qualified subject will be asked to schedule a study date to participate at home. The nights of sensor wear do not need to be consecutive. Subjects will be instructed to set-up both devices on Night One of sleep testing and then only the ANNE device on Nights 2-4.
One Night = HST and ANNE Sleep
3 Additional Nights = ANNE Sleep only
The target time frame will be to complete the sleep nights within 8 weeks of enrollment.
- (3) Subjects will be advised to avoid alcohol and sleep medication use such as antihistamine (OTC) or prescribed medicines for sleep support on the testing night. Any use of these substances on the night of monitoring sleep will be asked to be recorded in the diary.
- (4) Subjects will be informed how to complete the Demographic, Medical History and Sleep Survey sleep diary and usability survey (**Appendix A-C**). The surveys should be available to complete via an email link through REDCap or printed out forms.

Any subject's questions or concerns associated with the study will also be addressed.

At least 24 hours prior to the subject's sleep nights, the study coordinator will contact the participant by phone to confirm their planned sleep study nights at home.

The below sections describe the procedures for setting up the ANNE and HST devices, respectively.

8.1.3 ANNE™ Sleep procedures

The ANNE™ Sleep sensors will be applied by the study subjects themselves.

- 1) The PI or study coordinator will ensure the ANNE™ Sleep sensors are functional and collecting data properly prior to providing to subjects. The study coordinator will provide instructions for use of the ANNE™ Sleep system in the subject study kit.
- 2) Sensor placement (to be completed by the subject):
 - a) Using IPA alcohol wipes, the subject will wipe down the areas of the skin where the sensors will be placed thoroughly to remove any dirt, oils, etc. IPA alcohol wipes will also be used to clean the surface of the sensors before placement. If necessary, the subject may need to shave their chest to provide better adhesion and comfort of the sensor.
 - b) The subject will apply a single use adhesive to the chest sensor and place it on their chest at the suprasternal notch (see Figure 2). The subject will

STU#: STU00214445

attach the limb sensor to their finger using a single-use adhesive (see Figure 2).

[figure not shown]

Figure 2. Placement of the ANNE™ chest and limb sensors

3) Setting up a mobile device with an ANNE Sleep application

- a) The subject will pair the ANNE™ Chest and ANNE™ Limb sensors with the ANNE Sleep mobile application by following the instructions on mobile device
- b) After checking that the sensors are placed correctly and the signal quality is adequate, subjects will then proceed to sleep.

4) Data collection and storage

- a) After a full night of data collection, data will be collected through the ANNE Sleep application. The subject will download the data from the sensor through Bluetooth.
- b) The data will be uploaded automatically to ANNE™ Hub, a secure data repository from the application, and will be associated with the subject ID.
- c) The data will be stored in an EDF data format for further analysis.

8.1.4 WatchPAT One Procedures

The device along with a user manual and quick start guide will be provided to the participant. Participants will be instructed to follow the safety instructions in the user manual.

The procedures for the WatchPAT ONE are as follows (to be completed by the subject):

STU#: STU00214445

1. Subject will download the WatchPAT One mobile application on their mobile device.
2. Subject will strap the WatchPAT device to their non-dominant hand.
3. Subject will place the chest sensor
 - a. Subject will thread the chest sensor through the sleeve of their shirt.
 - b. Subject will peel the liner from the adhesive and attach the chest sensor to the chest under the sternal notch.
4. Subject will place the finger probe
 - a. Subject will insert a finger on the non-dominant hand into the Finger Probe until they feel the tip of the probe
5. Subject will press the START button on the application to begin data collection.
6. After a night of sleep, the subject will press the END RECORDING button on the application.

8.2 COMPLETION OF THE STUDY

- (1) After completing data collection, subjects will be given surveys (**Appendix C**) to complete in print material or by email link via a secure online platform managed by Northwestern University (i.e. REDCap).
- (2) Once the surveys and sleep nights are complete, the study coordinator will let the subject know that their participation is complete. The study coordinator will have a phone call with the subject to confirm testing was successful and address any issues if needed.
- (3) Subjects will be instructed to arrange for a time to return the study kit to the research team in person or will be provided with a pre-paid shipping label. A compensation gift card will then be mailed to the subject’s home address or given to them in-person (if they return the study kits in person to the research team).

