| Objectives: | 
Analysis of diagnostic yield from multiple nights with ANNE Sleep
 
 ● Analysis of agreement for diagnosis of moderate to severe OSA by determining a patient’s Apnea-Hypopnea Index (AHI) wearing the ANNE Sleep system and WatchPAT ONE over one (1) night worn concurrently ● Assessment of usability compared to current HST in the intended population |
| Investigational Product and Planned Use | ANNE™ Sleep System |
| Commercial Available HST Device | WatchPAT ONE |
| Statistical Analysis | Three subsequent nights will be with the ANNE Sleep system alone. Patient preference will be elicited via psychometric surveys for comfort |

STU#: STU00214445

| | |
|--|---|
| | 
and usability comparing ANNE and a commercially available Home Sleep Test (HST). We expect completion of this aim in 6 months. The apnea-hypopnea index (AHI) will be calculated in ranges of 15 – 30 apnea/hypopnea events per hour for moderate OSA and ≥ 30 apnea/hypopnea events per hour for severe OSA. The oxygen desaturation index (ODI), the hourly average number of desaturation episodes, will also be calculated. With a sample size of at least 30, the large amount of within-person data provides high statistical power for all planned analyses, allowing this data set to answer all proposed questions while minimizing study costs and any risk to patients.
 |
|--|---|

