4.1 Primary Outcome Measures

- Analysis of variation between nights of AHI derived from ANNE Sleep system across multiple sleep nights at home
- Analysis of agreement for diagnosis of moderate to severe OSA by determining a patient's Apnea-Hypopnea Index (AHI) wearing the ANNE Sleep system and WatchPAT ONE over one (1) night worn concurrently
- Patient responses on psychometric surveys for comfort and usability comparing ANNE Sleep and WatchPAT ONE

•

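### The primary comfort and usability comparison rates WatchPAT ONE after one joint night and ANNE Sleep after up to four nights, in a fixed order and only at End of Study, so device cannot be separated from exposure, recency and solo wear

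*Combined protocol and SAP*

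**What the plan says.** Section 4.1 lists this among three primary outcome measures: "Patient responses on psychometric surveys for comfort and usability comparing ANNE Sleep and WatchPAT ONE".

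The order of wear is the same for everyone. Section 8.1.2 says "Subjects will be instructed to set-up both devices on Night One of sleep testing and then only the ANNE device on Nights 2-4" and lists "3 Additional Nights = ANNE Sleep only". The Protocol Summary agrees: "Three subsequent nights will be with the ANNE Sleep system alone". The second primary outcome also describes the WatchPAT night as a joint one: "wearing the ANNE Sleep system and WatchPAT ONE over one (1) night worn concurrently". No WatchPAT-only night and no varied or randomised order is planned.

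On spacing, section 8.1.2 says "The nights of sensor wear do not need to be consecutive" and "The target time frame will be to complete the sleep nights within 8 weeks of enrollment".

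On the survey, section 8.2 says "After completing data collection, subjects will be given surveys", on paper or by email link through REDCap. The 7.1.4 schedule has a single usability tick, under End of Study. The night columns carry the sleep diary but no usability form. Section 10.2, item 3, gives the preference comparison one sentence, and nothing in 10.1 to 10.3 deals with order, exposure or recall.

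**The concern.** Each subject meets the two devices under different conditions and rates them only after those conditions have diverged. By then the subject has practised setting up ANNE more often, has used it more recently and has slept with it alone. WatchPAT was met once, first, and as half of a double set. A difference in ratings could come from the devices or from any of these conditions.

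Because this is a primary outcome, the study may report a preference, or a lack of one, that belongs to the schedule rather than to the device. The problem would remain with a perfectly matched questionnaire answered by every subject, so it is distinct from the question of what the survey asks.

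**Working it through.** The plan gives no power, effect size or test for this outcome. Section 10.1 claims only high power with at least 30 subjects. There is therefore no stated figure to reproduce, and the check is mainly a reading of the schedule.

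**Step 1: exposure when the rating is given (sections 8.1.2, 8.2, 7.1.4 and 11)**

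| | ANNE Sleep | WatchPAT ONE |
|---|---|---|
| Nights worn, four-night completer | 1 + 3 = 4 | 1 |
| of which alone | 3 | 0 |
| Nights worn, two-night completer (section 11) | 1 + 1 = 2 | 1 |
| of which alone | 1 | 0 |
| Place in the sequence | first and last | first only |

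Every subject has the same order, so no contrast between subjects or between nights can estimate the effect of order, practice or solo wear. The exposure ratio can vary with completion (4:1 or 2:1), but who completes is self-selected and WatchPAT exposure is 1 in every case. A larger sample narrows the interval around the same confounded quantity. The many within-person data that section 10.1 relies on are extra ANNE nights. They add nothing on WatchPAT.

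**Step 2: is joint wear a material condition?** Section 8.1.3 puts the ANNE chest sensor at the suprasternal notch, and section 8.1.4 puts the WatchPAT chest sensor under the sternal notch. Each device also has a finger sensor and its own application. The only WatchPAT night therefore carries two chest sensors in nearly the same area, two finger sensors and two set-ups. ANNE is also experienced without that load.

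**Step 3: the recall gap.** Three ANNE-only nights always lie between the WatchPAT night and a four-night completer's survey. If the nights are consecutive, the gap is a few days. If they are spread out, it could reach several weeks. It is not fixed.

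**Step 4: sensitivity, on assumed values only.** Suppose each of 30 subjects names a preferred device and a two-sided 5% sign test is used. The plan specifies neither. The exact two-sided p is 2 × P(X ≥ r) with X ~ Binomial(30, 0.5). For r = 20 it is 0.099 and for r = 21 it is 0.043, so 21 of 30 are needed. If the devices are truly equal but conditions move the observed ANNE share to p, the chance of a result favouring ANNE is P(X ≥ 21 | 30, p):

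| Assumed observed share for ANNE | Chance of a result favouring ANNE |
|---|---|
| 50% (no shift) | 2.1% |
| 55% | 6.9% |
| 60% | 17.6% |
| 65% | 35.8% |
| 70% | 58.9% |

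The table is symmetric: a shift to 40% gives the same 17.6% chance of a result favouring WatchPAT. It shows how sensitive such a comparison would be to a shift. It does not show that a shift of any given size occurs.

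**Step 5: would earlier timing alone be enough?** No item in Appendix B names WatchPAT. Item 1 asks about all the sensors together and item 4 about other sleep sensors in general. The rest concern ANNE, the wireless sensors, or sleep and home monitoring in general. Sending this form earlier would still not give a paired rating.

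**The case against.** The strongest reply is that an overall rating after several nights of home use is a legitimate target. The objectives concern multi-night use of ANNE and usability against current home testing, and section 10.2 plans no hypothesis test or superiority claim for preference. This stands as a reason to keep the end survey. It does not rescue the device comparison, because WatchPAT has no multi-night use to rate.

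A second reply is that, with no WatchPAT item in Appendix B, there is no device rating to bias. That is a real and separate gap. Filling it would leave the sequence problem in place, so the two must be fixed together.

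A third is that section 11 ties payment to nights with corresponding surveys, which might mean that more than one usability survey is intended. The term is undefined and could mean the nightly diaries. The schedule shows no usability form after Night One.

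Three stronger readings are tempting, and the documents do not support them:

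- **That the bias favours ANNE.** Practice and recency may, but section 13 lists skin irritation, rash and possible injury on removal for the ANNE adhesive. Repeated adhesive wear could lower its ratings.
- **That WatchPAT is recalled over about 8 weeks.** The target runs from enrollment and covers all the nights, and Night One comes after enrollment, scheduling and a call at least 24 hours ahead. Within target, the span from Night One to the last night is shorter than 8 weeks.
- **That ANNE is rated the morning after its last night.** Section 8.2 sets no deadline for returning the survey.

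**Conclusion.** The point holds as a design defect in a primary outcome. At the time of rating, exposure is 4 nights against 1 (or 2 against 1 for a two-night completer) and solo wear is 3 against 0 (or 1 against 0), with WatchPAT always the earlier experience. Device is confounded with number of exposures, recency and solo wear, and the planned data cannot undo this.

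The size and direction of any resulting bias are unknown, and the sign-test figures rest on assumed shares and an assumed test. The conclusion assumes that the 7.1.4 schedule, with its single usability tick, governs when the survey is given.

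**What to change.** 1. In section 8.2 and the 7.1.4 schedule, add a short usability survey for the morning after Night One, sent by the existing REDCap link.
2. Give it matched items that rate ANNE Sleep and WatchPAT ONE separately, for example on comfort, application and removal. Without these the earlier timing achieves nothing.
3. In sections 4.1 and 10.2, name this rating, taken when each device has had exactly one night, as the source for the ANNE versus WatchPAT comparison. State that the comparison is under concurrent wear and that no claim is made about WatchPAT worn alone.
4. Keep the End of Study survey as an ANNE-only measure of multi-night usability.
5. While editing, reconcile the appendix reference: section 8.2 points to Appendix C, which is the demographic, history and diary form, whereas the usability form is Appendix B. Also say what the surveys in section 11 are.

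The cost is one extra short form per subject, the drafting of the matched items and one schedule tick, with no added nights or subjects. The remaining limitation is that both devices are still rated while worn together, which the restated outcome discloses. The change needs to be in place before Night One, since a rating at equal exposure cannot be recovered afterwards.

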7.1.4 Checklist for scheduled events

The study coordinator should review the schedule of events, summarized below:

| | Initial Visit Day: Screening/ Enrollment | ANNE™ and HST Night One | ANNE™ ONLY Night Two, Three, and Four | End of Study* |
|--|---|-----------------------------------|---|---------------|
| Eligibility | X | | | |
| Consent | X | | | |
| Demographics, Medical Hx, STOP-BANG Questionnaire | X | | | |

STU#: STU00214445

| | | | | |
|---|--|---|---|---|
| ANNE™ Sleep | | X | X | |
| HST Sleep | | X | | |
| Sleep Diary | | X | X | |
| Phone follow-up (which may occur up to 1 week after the study) | | | | X |
| Usability Survey | | | | X |
| Adverse Events | | X | | X |

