12. WITHDRAWAL OF PARTICIPANTS

Participants may end their participation at any time during the study. The study investigators may choose to withdraw a study subject if he or she is unable to use the devices or complete the study procedures. The study investigators may withdraw a patient if they develop skin sensitivity or have a medical complication that precludes wearing of the sensors on the suprasternal notch.

If a subject is withdrawn from the study, they will be asked to return the study kit that is given to them at the start of the study. Unless specifically requested in writing, researchers will maintain and use data from patients that end their participation early.

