14. ADVERSE EVENTS

The PI will determine whether adverse events are related to the study or unrelated to the study. The length of the study will be 4 nights. All serious adverse events – even if not deemed to be study-related – will be reported to the IRB. This includes a participant's death, life-threatening condition, hospitalization, or disability. All study-related adverse events determined by the PI as serious will be recorded and reported to the IRB and the sponsor within 1 business day. Serious study-related adverse events are defined as adverse skin effects that warrant prescription medical therapy, skin tears leading to bleeding or an open wound, or skin burns. Study-related adverse events will be recorded on the adverse event form. If participation is discontinued, the timing of this will be recorded.

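### No adverse event check is scheduled at the time of Nights Two to Four, the three ANNE-only nights; they are covered only in retrospect at End of Study

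*Combined protocol and SAP*

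**What the plan says.** The schedule in section 7.1.4 has four columns: screening, Night One with both devices, a combined column headed "ANNE™ ONLY Night Two, Three, and Four", and End of Study. The adverse event row is "Adverse Events | | X | | X", so the third column is empty.

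Section 8.1.2 describes the ANNE-only period as "3 Additional Nights = ANNE Sleep only" and adds two timing rules: "The nights of sensor wear do not need to be consecutive", and "The target time frame will be to complete the sleep nights within 8 weeks of enrollment". Under section 7.1.4 the closing phone call can come as much as a week later.

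Three other sections use knowledge of skin events:

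- Section 12 on withdrawal: "The study investigators may withdraw a patient if they develop skin sensitivity".
- Section 13 names irritation, rash, injury on removal and allergic reaction to the ANNE adhesive as the device risks. It allows the sensors to be taken off for marked discomfort or rash.
- Section 14 describes a four-night study and names an adverse event form. It gives no time points or method of enquiry. Study-related events that the investigator judges serious "will be recorded and reported to the IRB and the sponsor within 1 business day".

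**The concern.** The nights without a scheduled check are the ones on which the investigational device is worn alone, at home and unsupervised. The subject applies new single-use adhesives each time (sections 6 and 8.1.3). On Night One the WatchPAT chest sensor is also stuck on just below the sternal notch (section 8.1.4), near the ANNE chest site. Nights Two to Four therefore give the cleaner view of ANNE skin tolerability.

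If the schedule is followed as written, a reaction that the subject does not volunteer comes to the team's notice only at End of Study. By then further adhesives may have been applied, and the night of onset rests on recall. The discretionary withdrawal in section 12 and the seriousness determination in section 14 both need the team to know of the event. No scheduled step between Night One and End of Study is designed to tell them.

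**Working it through.** The plan gives no figure to reproduce. The check is a reading of the schedule against the other sections, followed by simple arithmetic.

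**1. Is the blank cell real?** In the same table the diary row is "Sleep Diary | | X | X", with its second mark in the Nights Two to Four column. The ANNE wear row is also marked there. The table was therefore read with its columns intact, and the adverse event cell is empty.

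**2. Does another section fill the gap?**

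- Section 8.1.2: the coordinator phones at least 24 hours ahead, to confirm the planned nights. No adverse event enquiry is stated.
- Appendix A diary: sleep items and an optional comments field (item 15). It has no skin or adverse event item.
- Appendix B, item 10: asks about redness, irritation, both or none with the wireless sensors. Section 7.1.4 schedules the usability survey at End of Study only. The item records neither night nor severity, and questions may be skipped.
- Section 8.2: the closing call is to confirm that testing worked and to deal with any issues.
- Section 14: an adverse event form, without time points.

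None of these schedules an enquiry at the time of Nights Two to Four.

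**3. Share of exposure.** 3 of 4 wear nights = 75%. With the planned minimum of 30 completers, 30 × 3 = 90 of 30 × 4 = 120 person-nights.

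**4. Lag from a Night Two reaction to the next scheduled check.** Lag = (days from Night Two to Night Four) + (days from Night Four to End of Study).

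- Consecutive nights, End of Study at once: 2 + 0 = 2 days.
- Consecutive nights, call a week later: 2 + 7 = 9 days.
- Nights spread over the window: the 8 weeks (56 days) run from enrollment. If Night Two falls d days after enrollment and Night Four on day 56, the lag is (56 − d) + 7 = 63 − d days. Night One must come before Night Two, so d is above zero and the lag is just under 9 weeks at most. As an illustration, d = 14 gives 49 days, or 7 weeks.

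The 8 weeks are a target, so a longer lag is not excluded. The documents do not say how the nights will in practice be spaced.

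**5. Further nights of fresh adhesive before the next scheduled check,** if all four nights are worn and nothing is volunteered:

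- Night One reaction that appears after that night's check: 3
- Night Two reaction: 2
- Night Three reaction: 1
- Night Four reaction: 0

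**The case against.** A reader might infer from the blank cell that three nights have no safety assessment at all. The documents do not support that. The End of Study tick, the closing call and survey item 10 all cover those nights in retrospect. Section 14 does not confine recording to ticked visits. A subject may also report unprompted, write in the diary's comments field, mention a reaction on the call before the sleep nights, or take the sensors off. What these channels lack is a planned question at the time.

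A reader might also infer that the one-business-day rule would be broken. It would not. The rule covers study-related events that the investigator has determined to be serious, and it states no clock from onset. Ordinary redness falls outside it. Events that need prescription treatment, open wounds and burns are those most likely to be volunteered.

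Nor is it right that End of Study data cannot be tied to ANNE. Item 10 asks about the wireless sensors, the survey's term for ANNE. It loses the night and the severity, not the device.

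Three further limits stand. The adverse event form is not among the documents and the consent pages were removed, so an instruction to report reactions may exist unseen. Section 11 speaks of surveys accompanying the nights, which leaves some doubt about survey timing, although section 7.1.4 marks the usability survey only at End of Study. Section 13 classes the study as minimal risk and states that the adhesives passed biocompatibility and sensitization testing.

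**Conclusion.** The point holds as a minor gap in the timing of safety ascertainment. As written, the schedule plans no adverse event check at the time of Nights Two to Four, and neither the procedures nor the appendices supply one.

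The delay for a Night Two reaction ranges from about 2 days to just under 9 weeks. The upper end assumes an early Night Two, a Night Four at the end of the target window, a closing call a full week later and no spontaneous report. A delay of weeks is therefore possible but not established. Reapplication before the next check concerns reactions from Nights One to Three only.

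What is affected is when the withdrawal provision and the seriousness determination can operate, and whether an event can be placed on a night. No primary outcome in section 4.1 depends on adverse events, which section 10.3 only lists by subject.

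**What to change.** - Mark Adverse Events in the Nights Two to Four column of section 7.1.4.
- Add one line to the Appendix A diary, already completed on those nights, asking about skin reactions or other adverse events, with a prompt to contact the coordinator. The diary's date then fixes the night.
- Reconcile the schedule with sections 12, 13 and 14, stating when and how adverse events are collected across all four nights. In the same edit, correct section 8.2, which cites Appendix C for the end-of-study surveys although the skin item is in Appendix B.

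This changes data collection only; no clinical rule is proposed. The cost is one table cell, one diary line, a few sentences of text, and a few more minor events to log.
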